8.7 ARDS animal model study with Ibudilast

In this study, ibudilast was tested in a LPS-induced neonatal ARDS animal model to evaluate its anti-inflammatory effect. Ibudilast ameliorated LPS-induced pathological manifestations and pulmonary edema in lung tissue. In addition, ibudilast attenuated the secretion of inflammatory cytokines TNF-alpha, IL-1 beta, IL-6 and MCP-1 by inactivating the chemokine axis and significantly reduced LPS-induced cell apoptosis in lung tissue ([Yang et al 2020](#)).

8.8 Previous Human Experience

Ibudilast is approved in Japan and South Korea for treatment of asthma (20 mg/day) and post-stroke dizziness in cerebrovascular disorders (30 mg/day) and has been prescribed for these indications for almost 30 years. The largest accumulation of clinical safety experience with ibudilast (MN-166) is from the approval of Ketas® for asthma and post-stroke dizziness. Dosing was 20 to 30 mg/day (included uses up to 40 mg/day) and based on chronic administration. In the [Ketas package insert](#), the most common adverse events were anorexia (0.6%), nausea (0.6%), increased liver enzymes (ALT 0.4%, AST 0.3%, and GTP 0.4%). Following regulatory approval, adverse event data continued to be collected and, to date, approximately 14,968 subjects were evaluated. Safety data was taken from the 2009 Ketas package insert and Interview Forms collected from 1989 to 1996. Seven hundred sixty-nine (769) adverse drug reactions occurred in 507 (3.39%) patients. The most common ($\geq 5\%$) adverse drug reactions were: itching (8; 0.05%), rash (8; 0.05%), abdominal pain (7; 0.05%), heavy head feeling (7; 0.05%), stomach

pain (7; 0.05%), epigastric discomfort (8; 0.5%), BUN increased (7; 0.05%), heart rate/heart rhythm disorders (8; 0.05%), vertigo (10; 0.7%), serum cholesterol increased (10; 0.07%), general malaise (10; 0.07%), lack of appetite (13; 0.09%), headache (13; 0.09%), heartburn (16; 0.11%), vomiting (19; 0.13%), nausea (22; 0.15%), stomach discomfort (24; 0.16%), ALP increased (36; 0.24%), AST increased (45; 0.30%), ALT increased (53; 0.35%), sickness (54; 0.36%), gamma-GTP increased (54; 0.36%), and anorexia (71; 0.47%).

9.0 CLINICAL OVERVIEW

To date, ibudilast has been evaluated in a total of 21 ongoing and completed clinical trials; 11 clinical trials by the sponsor and 10 trials by investigator and more than 750 subjects have been exposed. Eight investigator-initiated studies are conducted or ongoing in US cross-referenced to sponsor's IND. Two trials were conducted in Australia, one study targeted medication overuse headache (Australian CTN File No. 2011/012799) and the other targeted chemotherapy-induced-peripheral neuropathy (Australian CTN File No. 2018/010601). An overview of the safety profile in each of the Phase 2 clinical trials will be reported below.

9.1 MediciNova-Sponsored Studies

Among 10 completed Phase 1 and 2 studies, more than 620 received ibudilast up 100 mg/d in single and multiple doses up to 2 years.

Ibudilast was tested at dosages of 30 or 60 mg/d up to 2 years in the Phase 2 clinical trial (MN-166-CL-001) with relapsing-remitting multiple sclerosis (RRMS) patients. A total of 297 subjects were randomized; of those, 103 subjects were randomized to placebo, 95 subjects were randomized to 30 mg/d, and 99 subjects were randomized to 60 mg/d. A total of 291 subjects received ibudilast 30 mg/d or 60 mg/d for up to 2 years in the open-label-extension phase. The most common treatment related AEs were nausea, headache, and upper respiratory tract infection. There were 20 SAEs reported during entire 2-year duration of the study. All SAEs were considered not related to ibudilast in this study.

In the Phase 2 SPRINT-MS/NN102 trial, a total of 255 progressive MS subjects were enrolled, 129 subjects received doses of ibudilast up to 100 mg/d and 126 subjects received placebo for up to 96 weeks. Safety results of study SPRINT-MS/NN102 suggests that the adverse event profile of ibudilast appears to be similar to the pattern of events seen in the MN-166-CL-001 study at daily doses up to 100 mg/day. Most of the adverse events that appear to be related to ibudilast fall under the Gastrointestinal SOC, nausea, vomiting diarrhea, abdominal pain, and dyspepsia. Other treatment-related adverse events included fatigue, hepatic enzymes increased, WBC decreased, alanine aminotransferase, headache, decreased appetite, and insomnia. Although there was a higher incidence of depression in the ibudilast group, most of the events were considered to be unrelated by the principal investigator. There were 58 SAEs reported in 44 subjects across both treatment groups during the 96 weeks trial. One SAE of ataxia was considered related to ibudilast, which was a single event and resolved the next day.

In the Phase 1b/2a MN-166-ALS-1201 study, 45 subjects with ALS received ibudilast 60 mg/d for up to 52 weeks. Safety results of the MN-166-ALS-1201 study also show a similar profile to the MS studies. The most commonly reported adverse events fall under the Gastrointestinal and

Nervous System SOCs. The most commonly reported TEAEs in the ibudilast group were dysphagia, nausea, fatigue, pain, upper respiratory infection, fall, weight loss, anorexia, headache, depression, insomnia, cough, and dyspnea. Treatment-related events that were attributed to ibudilast were decreased/loss of appetite, anorexia/weight loss, nausea, and ECG changes (atrioventricular junctional rhythm), and increased QTcB to upper normal of 470 (Brooks et al 2017).

In the Phase 2 open-label study (MN-166-ALS-1202) a total of 35 subjects with ALS received 100 mg/day up to 9 months. The most commonly reported treatment-related adverse event was nausea.

These studies suggest that ibudilast at daily doses of up to 100 mg/d appear to be generally safe and well-tolerated. The most commonly reported AEs have been nausea, abdominal pain, diarrhea, and headaches. There was a slight dose-related increase in the percent of subjects with headaches and gastrointestinal AEs. The incidence of nausea suggested a dose-related increase. Ibudilast also appeared to cause transient changes in laboratory values, particularly AST, ALT and GGT which, in most cases, appeared to resolve over time.

9.2 Study Dose Justification

In a preclinical model of ARDS in mice, ibudilast 7.5 mg/kg i.p. treatment significantly reduced LPS-induced pathological changes and pulmonary edema in lung tissues. In addition, ibudilast treatment attenuated the secretion of inflammatory cytokines IL-1 β beta, IL-6, TNF, and MCP-1, and significantly reduced LPS-induced cell apoptosis in lung tissues.

Based on internal data, a 7.5 mg/kg dose of ibudilast administered i.p. resulted in an AUC of approximately 862 h*ng/mL, an exposure that is achieved in healthy volunteers at doses of 30-50 mg administered twice daily.

In ALS patients receiving ibudilast 100 mg per day orally, a significant reduction in MIF was observed after treatment. This effect was maintained throughout the 36-week duration of the study.

The safety of a single dose of 100 mg has been established in healthy volunteers. In addition, long term safety of up to 96 weeks of 100 mg/day doses has been established in MS and ALS patients without any significant safety sequelae. The 100 mg/day is the dose that is shown to exert significant reductions in MIF levels, and therefore considered the targeted clinical dose.

9.3 Treatment Duration Justification

According to CDC, among the COVID-19 patients who developed severe disease, the medium time to dyspnea ranged from 5 to 8 days, the median time to acute respiratory distress syndrome (ARDS) ranged from 8 to 12 days, and the median time to ICU admission ranged from 10 to 12 days. According to the published paper discussing a total of 191 COVID-19 patients treated in Wuhan, China, (Zhou et al 2020 Lancet), the median time from illness to dyspnea was 7.0 days, median time from illness to onset of ARDS was 12 days, and median time from illness to ICU admission was 12 days in total patients. The median time from dyspnea to intubation was 10.0 days (IQR 5.0–12.5) for patients who received invasive mechanical ventilation.

The steady-state plasma ibudilast concentrations are reached within 3 days of initiating b.i.d. and we want to treat at least 5 days with steady state drug level, thus, we determined duration of treatment to be 7 days.

10.0 TRIAL OBJECTIVES

10.1 Primary Objectives

The primary objectives of the study are to evaluate the:

- Efficacy of ibudilast vs. placebo in COVID-19 subjects measured by the proportion of subjects free of respiratory failure (i.e., decreased need for O₂ therapy) at Day 28;
- Efficacy of ibudilast vs. placebo in COVID-19 subjects measured by clinical status (i.e., improvement on NIAID scale) at Day 28;

10.2 Secondary Objectives

The secondary objectives of the study are to evaluate the:

- Safety and tolerability of ibudilast vs. placebo in COVID-19 subjects;
- Efficacy of ibudilast vs. placebo in COVID-19 subjects measured by the proportion of subjects free of respiratory failure (i.e., decreased need for O₂ therapy) at Days 7, 14, and 60;
- Efficacy of ibudilast vs. placebo in COVID-19 subjects by clinical response of ibudilast vs. placebo in COVID-19 subjects at Days 7, 14, and Day 60;
- Anti-inflammatory effects of ibudilast vs. placebo on cytokine levels;
- Pharmacokinetics of ibudilast vs. placebo in COVID-19 subjects.

11.0 OVERALL STUDY DESIGN

This is a randomized (1:1), double-blind, placebo-controlled, parallel-group study of ibudilast in hospitalized COVID-19 subjects at risk for developing ARDS receiving standard of care. The study will consist of a Screening Phase followed by a Treatment and Follow-up Phase.

Following the Screening Phase, if the subject meets eligibility criteria, subject will be randomly assigned treatment with MN-166 (ibudilast) or placebo. Upon completion of the 7-day Treatment Phase, subject will be followed-up at Day 14, Day 28, and Day 60. Subjects will receive ibudilast 100 mg/d (50 mg b.i.d) or matching placebo (50 mg b.i.d.) every day for 7 days. (See [Table 1](#) for study assessments).

11.1 Screening

The following screening assessments will be performed upon signing the ICF: inclusion/exclusion criteria review, physical exam, assess vital signs and O₂ use and SpO₂, clinical status using the NIAID scale, 12-lead ECG, draw blood for plasma biomarkers that include migration inhibitory factor (MIF), (interleukin 1-beta (IL-1 β), interleukin 6 (IL-6), tumor necrosis factor (TNF- α), C-reactive protein (CRP) and other exploratory biomarkers. A complete blood count (CBC), comprehensive metabolic panel (CMP), D-dimer and coagulation tests will

also be drawn. A serum pregnancy test will be done in pre-menopausal females. Prior concomitant medications taken within the last 7 days prior to study drug administration will be recorded.

11.2 Treatment Phase

During the Treatment Phase, hospitalized subjects will be treated with MN-166 or placebo for a 7-day period. During the Treatment Phase, subjects will undergo study-related procedures including physical exam, ECG, O₂ use assessment and SpO₂, biomarkers and PK samples (except Day 7) draw, CBC, CMP, D-dimer blood collection, clinical assessment using the NIAID scale, and information on adverse events and concomitant medications will be recorded (see [Table 1](#) Schedule of Assessments).

11.3 Follow-up

On Study Day 14, if subject is still hospitalized, the site will conduct physical examination, clinical status (NIAID scale), vital signs, O₂ use and SpO₂, CBC, CMP, D-dimer, coagulation tests, biomarkers, and AE and concomitant medications review.

On Study Day 28, subject's clinical status (NIAID scale) and survival status will be recorded, O₂ therapy status use, AE and conmed review. A telephone follow-up is permitted if subject is no longer hospitalized.

On Study Day 60, subjects will undergo the following assessments: clinical status using the NIAID scale, O₂ therapy status, survival status, AE and conmed review. In addition, vital signs, 12-lead ECG, and clinical safety labs (CBC, CMP, CRP, D-Dimer, PT and INR) will be performed in intubated subjects only.

11.4 Early Termination/Discharge from Hospital

If subject early terminates from the study or is discharged from the hospital on Days 2, 4, or 6, the site will conduct clinical assessment, take vital signs, O₂ use and SpO₂, draw biomarker sample, and review AEs and concomitant medications. If subject early terminates from the study or is discharged on Days 1, 3, 5, or 7, the site will conduct the study assessments scheduled on those days.

Subjects who are discharged prior to Day 7 will be given the remainder of their study medication to be taken at home and a pulse oximeter supplied by the sponsor to measure their O₂ levels once daily until Study Day 14.

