7.0 SCHEDULE OF ASSESSMENTS

Table 1 Schedule of Assessments

Phase	Screening	Double-Blind Treatment Phase ^{e,g}							Follow-up		
Study Day	Day -3	Day 1 BL	Day 2	Day 3	Day 4	Day 5	Day 6	Day 7	Day 14 ^e (± 3)	Day 28 (+/- 3)	Day 60 (+/- 7d)
Informed consent	X										
Inclusion/exclusion criteria review	X										
Brief physical exam	X	X		X		X		X	X		
Clinical status using NIAID scale	X	X	X	X	X	X	X	X	X	X	X
Vital signs (BP, RR, HR, Temp)	X	X	X	X	X	X	X	X	X		Xⁱ
O₂ therapy status and SpO₂	X	X	X	X	X	X	X	X	X	X	X
12-lead ECG	X	X^a		X^a		X^a		X^a			Xⁱ
Biomarker plasma samples: MIF, IL-1β, IL-6, TNF-α	X^b	X		X		X		X	X		
PK blood sample^c		X		X		X					
CBC, CMP, CRP, D-dimer, PT, INR	X^d	X		X		X		X	X		Xⁱ
Randomize^f	X										
Administer study drug		X^h	X	X	X	X	X	X			
Adverse event review		X	X	X	X	X	X	X	X	X	X

Prior/Concomitant medication review	X	X	X	X	X	X	X	X	X	X	X
Record survival status ^j									X	X	X

^a 12-lead ECG to be done between 2-4 hours after AM dose.

^b Biomarker blood sample collection at screening is optional if Screening and Day 1 assessments occur on the same day.

^c Collect PK samples on Day 1 in the AM prior to study drug dosing and at 2, 4, 8, and 12 hours (Predose of PM dose); Day 3 and Day 5 prior to AM study drug dosing. PK samples to be collected for 8 subjects only.

^d Serum β-hCG for pre-menopausal women.

^e Telephone follow-up if subject is not in hospital. If subject is no longer hospitalized or cannot return due to COVID restrictions, a telephone follow-up to record O₂ usage/levels, AEs and conmeds may be conducted. All other assessments are optional.

^f Subjects may be randomized during the Screening Phase after all of the screening assessments are completed and subject is considered eligible for the study or on Day 1.

^g If subject prematurely discontinues from the study or is discharged from the hospital on Days 2, 4, or 6 collect biomarker samples in addition to other scheduled assessments. If subject prematurely discontinues from the study or is discharged on Days 1, 3, 5, or 7, conduct the study assessments scheduled on those days.

^h The first dose of study drug may be started in the AM or the PM.

ⁱ Vital signs, ECG and safety labs will be done in intubated subjects only.

^j Survival status is captured on the NIAID questionnaire.

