14.2 Clinical Lab Testing

Clinical laboratory testing (CMP, CBC, and coagulation) will be performed at Screening, Day 1, Day 3, Day 5, Day 7, Day 14 and Day 60 (in intubated subjects only) at the site's local laboratory.

Table 4 CMP, CBC, and Coagulation Tests

Comprehensive Metabolic Panel (CMP)	Complete Blood Count (CBC) with Diff
Serum albumin	white blood cell count (WBC)
blood urea nitrogen (BUN)	white blood cell differential
calcium	eosinophilic leukocyte count
carbon dioxide (bicarbonate)	basophilic leukocyte count

chloride	neutrophil count
Serum creatinine	lymphocyte count
glucose	monocyte count
potassium	platelet count
sodium	red blood cell count (RBC)
total bilirubin	hemoglobin
total protein	hematocrit
alanine aminotransferase (ALT)	D-dimer
alkaline phosphatase (ALP)	PT
aspartate aminotransferase (AST)	INR
GFR (estimated- will be autocalc by database)	

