15.3 Treatment Phase

15.3.1 Day 1 (Baseline), Day 3, Day 5 and Day 7

- Brief physical exam
- Assess clinical status using NIAID scale
- Assess vital signs (BP, RR, HR, Temp),
- Assess O₂ use including invasive mechanical ventilation, non-invasive ventilation (CPAP, BiPAP, nasal cannula high-flow oxygen), or ECMO and SpO₂
- 12-lead ECG (check between 2-4 hours after AM dose of study drug)
- Collect blood sample for biomarkers (MIF, IL-1 β , IL-6, TNF α)
- Collect PK samples (except Day 7)
- Comprehensive Metabolic Panel (CMP), Complete Blood Count (CBC), CRP, D-dimer, PT, INR
- Adverse events review
- Concomitant medication review

- Administer study drug (Study drug is administered every day on Days 1 through 7)

15.3.2 Day 2, Day 4, and Day 6

- Assess clinical status using the NIAID scale
- Assess vital signs (BP, RR, HR, Temp)
- Assess O₂ use including invasive mechanical ventilation, non-invasive ventilation (CPAP, BiPAP, nasal cannula high-flow oxygen), or ECMO and SpO₂
- Administer study drug
- Adverse events review
- Concomitant medication review

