15.3.4 Early Termination/Discharged from Hospital

If subject is no longer hospitalized or cannot return due to COVID restrictions, a telephone follow-up to record O₂ usage, AEs and conmeds taken will be conducted. All other assessments are optional.

If subject terminates early from the study or is discharged from the hospital prior to completion of the Treatment Phase, complete assessments scheduled for that Study Day. If subject discontinues or are discharged on Days 2, 4, or 6, collect a biomarker sample in addition to their regularly scheduled assessments.

Subjects who are discharged prior to Day 7, will be given their study medication to be taken at home and a pulse oximeter (ClinicalGuard CMS-50DL Fingertip Pulse Oximeter) supplied by the sponsor to record their O₂ saturation once daily until Day 14.

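### Discharge on Day 2, 4 or 6 calls for a biomarker draw but no CBC or CMP before home dosing, so one cheap last check against the lab stopping limits is missed

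*Combined protocol and SAP*

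**What the plan says.** Protocol section 11.4 covers discharge on Days 2, 4 or 6. It lists a clinical assessment, vital signs, oxygen use and saturation, and then asks the site to "draw biomarker sample, and review AEs and concomitant medications". Section 15.3.4 agrees: "If subject discontinues or are discharged on Days 2, 4, or 6, collect a biomarker sample in addition to their regularly scheduled assessments". So does Table 1 footnote g, for a subject who "is discharged from the hospital on Days 2, 4, or 6 collect biomarker samples in addition to other scheduled assessments".

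The regular schedule adds no safety labs on those days. Section 15.3.1 lists "Comprehensive Metabolic Panel (CMP), Complete Blood Count (CBC), CRP, D-dimer, PT, INR" for Days 1, 3, 5 and 7; section 15.3.2, for Days 2, 4 and 6, has no such line.

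Under section 11.4, subjects leaving before Day 7 are "given the remainder of their study medication to be taken at home". No section makes that supply depend on a laboratory result.

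After discharge, Table 1 footnote e (attached to the treatment-phase header and to Day 14) and section 15.3.4 provide for telephone contact and state: "All other assessments are optional". The condition in 15.3.4 reads "If subject is no longer hospitalized or cannot return due to COVID restrictions", which looks like a pandemic accommodation. Section 14.2 gives its list with no exception for discharged subjects: "Clinical laboratory testing (CMP, CBC, and coagulation) will be performed at Screening, Day 1, Day 3, Day 5, Day 7, Day 14".

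**The concern.** The laboratory stopping limits work only if the tests are done. Section 9.1 lists raised hepatic enzymes and decreased white cells among the treatment-related events at up to 100 mg/day, the dose used here. Such changes can be silent, so a telephone review of adverse events may miss them.

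An inpatient on Day 2, 4 or 6 has another required CBC and CMP the next day. A subject discharged that day may have none for the rest of the course, although blood is being drawn at discharge anyway. That sample goes to a central laboratory for cytokines and related markers (section 14.3), none of which appears in the stopping limits.

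There is also a small reporting cost. Protocol section 19.3 makes laboratory changes secondary endpoints, and SAP section 11.3 plans shifts to the last, highest and lowest values. A Day 2 leaver may have no post-baseline value to contribute.

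**Working it through.** **1. Which panels feed the limits.** Sections 12.7 and 13.5 give the same five limits. Matched to Table 4 in section 14.2:
- CMP: AST, ALT or total bilirubin above 3 × ULN; bilirubin above 3 mg/dL; albumin below 28 g/L.
- CBC: white cells below 2500/mm³; platelets below 75,000/mm³.

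That is three from the CMP and two from the CBC. Without these panels none of the five can be checked.

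**2. Last required lab.** CBC and CMP fall on Days 1, 3, 5 and 7, and SAP section 7.3 gives Days 2–7 a window of 0 days. The last required lab before discharge on Day 2, 4 or 6 is therefore Day 1, 3 or 5.

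**3. Uncovered stretch.** Gap = last dosing day − day of last required lab. Under section 13.0 the last dosing day is Day 7 with an AM start and Day 8 with a PM start. For a Day 2 discharge with an AM start, the gap is 7 − 1 = 6 days now and 7 − 2 = 5 with a discharge-day lab.

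**4. Doses still to take.** The course is 2 × 7 = 14 doses. For discharge on Day d after the morning dose, 2d − 1 doses have been taken with an AM start, leaving 15 − 2d. With a PM start, 2d − 2 have been taken, leaving 16 − 2d.

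| Discharge day | Last required lab now | Required labs after Day 1, now → fix | Gap in days, AM start | Gap in days, PM start | Home doses of 14, AM (PM) start |
|---|---|---|---|---|---|
| 2 | Day 1 | 0 → 1 | 6 → 5 | 7 → 6 | 11 (12) |
| 4 | Day 3 | 1 → 2 | 4 → 3 | 5 → 4 | 7 (8) |
| 6 | Day 5 | 2 → 3 | 2 → 1 | 3 → 2 | 3 (4) |

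The last column is the same before and after the fix.

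**5. Discharges the fix does not touch.** Labs are already required on Days 1, 3 and 5. The same formulas leave 13 (14), 9 (10) and 5 (6) home doses, with AM-start gaps of 6, 4 and 2 days.

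**6. Reach.** SAP sections 13.1 and 13.2 record 31 + 5 = 36 subjects consented; SAP section 3.1 plans approximately 40.

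**The case against.** The strongest reply is that this is a consistent scheduling choice. The three discharge rules agree with each other, and every inpatient doses on Days 2, 4 and 6 on the previous day's result. Existing safeguards also cover part of the gap: section 13.5 requires a repeat within 24 hours after an out-of-limit value, exclusion criterion 5 applies the same limits at entry, and the adverse-event stopping rules and safety monitor continue. Exposure is short, and section 9.1 reports that enzyme changes mostly resolved.

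Much of this stands. A reader might infer that supplying drug on a day-old lab is itself the fault. The documents do not support that, because the interval is the normal one. What differs is that no further lab need follow. The section 13.5 repeat is also why the Day 2 statement is limited to subjects whose Day 1 values were within limits.

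A reader might also take the 11 or 12 of 14 home doses after a Day 2 discharge (79% or 86%) as what an added draw would cover. It would not. Those doses are taken at home either way, and only the start of the uncovered stretch moves.

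Nor does timing to steady state add much. Section 9.3 puts steady state within 3 days. A Day 4 morning draw is about 72 hours in with an AM start but about 60 with a PM start, and a Day 2 morning draw is about 24 or 12 hours in. Nothing in the documents says that laboratory changes wait for steady state.

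The reply does not show a reason to leave the panels off a draw that is already being taken.

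**Conclusion.** The gap is real and small, and the change is worth considering. Subjects discharged on Day 2, 4 or 6 go home with study drug and may not be checked again against the laboratory limits. Adding the panels gives one more required check and shortens the unmonitored stretch by one day. It also secures a post-baseline value for a Day 2 leaver, though not one inside the Day 7 window.

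This rests on three assumptions:
- Footnote e and section 15.3.4 govern after discharge. If section 14.2 were read as overriding them, labs would still be due on the later scheduled days, but that fits poorly with telephone follow-up.
- The Day 1 draw is taken before the first dose. The protocol does not say so. If it is, a Day 2 leaver may have no on-drug lab at all.
- Discharge follows the morning dose, which affects only the dose counts.

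The documents do not give the number discharged on these days, so the number of subjects affected is unknown. The optional status of labs after discharge is a trade-off and is not faulted here. Nothing in the documents suggests that any subject was harmed.

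**What to change.** In section 11.4, section 15.3.4 and Table 1 footnote g, add CBC and CMP to the discharge draw on Days 2, 4 and 6 for subjects given home supply. Let a same-day routine-care result from the site's local laboratory count. Have the investigator review the result against section 12.7 before releasing the drug. If it is still pending, the review should follow as soon as the result is available, with a telephone call to the subject. Apply section 13.5 to any out-of-limit value.

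The cost is wording in three places, local-laboratory tubes at an existing draw, possibly a short wait for a result, and an occasional repeat test after discharge, which isolation rules may make hard to arrange. Monitoring during home dosing, or helping Day 1, 3 and 5 leavers, would need a return visit and is outside this change.

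With 36 of about 40 planned subjects consented, and SAP section 3.3 describing randomization in the past tense, few further subjects here may benefit. The wording is mainly for the future studies that SAP section 5 says this pilot will inform.
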